10.3 Method of collection of safety information

Safety information will be collected from the collaborating surgeons, through case report forms.

10.4 Frequency of data collection

Safety data collection starts when the patient signs informed consent. Data will be collected on the day of surgery, on the standardized data collection form which is separately uploaded. Data should be forwarded to the PI within 7 business days of collection. Adverse events should be reported within 7 business days.

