1.2 Primary Study Endpoints

The primary endpoint is the number of sentinel nodes correctly identified with ICG and fluorescence imaging alone.

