3.3 Early Withdrawal of Subjects

3.3.1 Criteria for removal from study

Subjects will be removed from the study if they withdraw consent prior to surgery. The study itself occurs only in the operating room, with no long term follow-up or involvement of the subject.

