7.2.2 Operative Procedure

When the subject is in the operating room and appropriately sedated or anesthetized, he or she will receive a dermal injection of indocyanine green (ICG) 0.9 ml at the melanoma tumor site or subareola if breast cancer. Incision is made in the axilla or groin, and the SPY machine is positioned over the lymph node basin. Real-time lymphangiography (SPY) is used to identify sentinel nodes. Any fluorescent nodes should be resected and are considered sentinel nodes. The absolute fluorescence will be quantified for each sentinel node. Absolute fluorescence is calculated by the SPY machine.

After the sentinel lymphadenectomy is complete but prior to closing skin, the excised lymph nodes will be examined with the gamma probe (detects tech99 signal) to confirm that they are sentinel nodes. If the node does not have a signal with the gamma probe (but is fluorescent) it is still considered a sentinel node. The lymph node basin will also be examined with the gamma probe, to insure that no sentinel nodes are missed. If a gamma positive sentinel node is identified in the lymph node basin, it should be resected and imaged with SPY. If no sentinel nodes are able to be identified with fluorescent imaging, the gamma probe will be used as per usual practice. The surgeon should spend no more than 30 minutes using SPY to identify sentinel

nodes. If after 30 minutes no sentinel node is found, the gamma probe should be used. The data collection form (separately uploaded) should be completed for each case.

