7.4.4 Subject Compliance Monitoring

All pertinent procedures and data collection will occur in the operating room. Subject compliance monitoring is not applicable for this study.

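### A fluorescent specimen counts toward the primary endpoint without any stated confirmation that it contains lymph node tissue (minor; cheap to improve)

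*Combined protocol and SAP*

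**What the plan says.** Section 1.2 states: "The primary endpoint is the number of sentinel nodes correctly identified with ICG and fluorescence imaging alone." Section 8.3 repeats this per patient and adds the number of patients in whom ICG alone succeeded. Neither section says against what *correctly* is judged, or what makes a patient a success.

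The counting rule is in section 7.2.2:

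- "Any fluorescent nodes should be resected and are considered sentinel nodes."
- After excision, "the excised lymph nodes will be examined with the gamma probe (detects tech99 signal) to confirm that they are sentinel nodes."
- A negative reading changes nothing: "If the node does not have a signal with the gamma probe (but is fluorescent) it is still considered a sentinel node."
- The basin is also scanned: "If a gamma positive sentinel node is identified in the lymph node basin, it should be resected and imaged with SPY." How such a subject is then scored is not stated.

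On timing, section 7.4.4 says "All pertinent procedures and data collection will occur in the operating room", section 10.4 says "Data will be collected on the day of surgery, on the standardized data collection form which is separately uploaded", and section 3.3.1 says "The study itself occurs only in the operating room, with no long term follow-up or involvement of the subject". No procedure, endpoint or analysis section mentions pathology. The word appears only in the institutional approvals checklist in 17.2.

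**The concern.** An endpoint that counts correct identifications needs something to be correct against. Here the surgeon's view of fluorescence decides what is excised and also what is counted. The one planned check on the excised tissue cannot remove a fluorescent specimen from the count.

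If a specimen taken as a fluorescent node turns out to hold no nodal tissue, two results are affected. The node count is one too high. If it was the subject's only fluorescent specimen, ICG failed in that subject, yet the rules allow a success to be recorded. The fallback to the gamma probe in 7.2.2 does not necessarily catch this, because it applies when fluorescence has found no sentinel node, and here the surgeon believes that one has been found.

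At stake is the study's central question in 1.1, whether ICG alone is enough. The error runs in the favourable direction.

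**Working it through.** **1. The plan's own figure.** Section 8.1 gives 20 + 20 = 40 subjects, which adds up. Section 8.2 calls this a convenience sample. There is no alpha, power, margin or success threshold, so there is no design calculation to reproduce.

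**2. Following one specimen through the rules.** Take a fluorescent specimen without nodal tissue, excised as a node.

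- Rule for counting (7.2.2): it fluoresced and was taken as a node, so it counts.
- Gamma check on the specimen (7.2.2): if negative, it still counts.
- Gamma check on the basin (7.2.2): this may reveal a true node left behind, which is resected and imaged, but no sentence turns the subject into a failure.
- Later correction (3.3.1, 7.4.4, 10.4): collection is placed in the operating room on the day of surgery, and no later step is described.
- Endpoint and analysis (1.2, 8.3): no confirmation is required.

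The specimen therefore stays in the count.

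**3. Scale at node level.** Inputs: 40 subjects (8.1) and a mean of 1.87 ICG nodes per patient (2.1). That mean comes from a trial in which every subject received all three tracers, so using it for ICG alone is an assumption. Expected specimens: 1.87 × 40 = 74.8, about 75. The documents give no node-free rate q, so a range is assumed. Expected miscounted specimens are 75 × q. The chance of at least one is 1 − (1 − q)^75, taking specimens as independent.

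| Assumed q | Expected miscounted | Chance of at least one |
|---|---|---|
| 1% | 0.75 | 53% |
| 2% | 1.5 | 78% |
| 5% | 3.75 | 98% |

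**4. Scale at patient level.** Only subjects with a single fluorescent specimen can change from success to failure through one node-free specimen. Their number m is not given. Assume 30%, 40% or 50% of 40, so m = 12, 16 or 20. The chance of at least one affected subject is 1 − (1 − q)^m.

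| Assumed q | m = 12 | m = 16 | m = 20 |
|---|---|---|---|
| 1% | 11.4% | 14.9% | 18.2% |
| 2% | 21.5% | 27.6% | 33.2% |
| 5% | 46.0% | 56.0% | 64.2% |

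**5. Effect on the reported rate.** One subject is 1/40 = 2.5 percentage points. With exact (Clopper-Pearson) 95% intervals:

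- 40/40 = 100% (91.2 to 100)
- 39/40 = 97.5% (86.8 to 99.9)
- 38/40 = 95.0% (83.1 to 99.4)

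One or two reclassified subjects shift the estimate by less than the width of these intervals.

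**The case against.** Four points can fairly be made on the other side.

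- **The form was not available.** The data collection form is uploaded separately and may already hold a pathology field. This stands: a reader might infer that the count is never checked against pathology, and the documents cannot show that. But a field on a form would not change 1.2 and 8.3, which do not say that it is used.
- **The timing sentences were written for other purposes.** Section 7.4.4 explains why compliance monitoring does not apply, and 10.4 belongs to the safety monitoring plan. This also stands. The weight rests on 7.2.2, with these sections as support.
- **The rule speaks of nodes, not specimens.** Read literally, non-nodal tissue does not qualify. True, but the surgeon applies the rule by eye and the plan states no step that would detect a mistake.
- **The gamma scan of the basin is a safeguard.** It may expose a true node left behind. It does not remove the wrong specimen from the count, and its effect on scoring is not stated.

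Three stronger readings are tempting and are not supported:

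- A reader might infer that a specimen holding several nodes also turns a failure into a success. It does not: that patient remains a success.
- A reader might infer that excising packets rather than single nodes distorts the comparison of surgeons. Section 8.3 follows each surgeon's success rate, and on the patient-level reading that rate does not depend on how many nodes a specimen holds.
- A reader might infer that the pathology node count should replace the surgeon's count. Pathology cannot show which node in a packet fluoresced, so ICG would be credited with non-fluorescent neighbours.

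**Conclusion.** The point holds in a limited form. As written, the plan lets a node-free fluorescent specimen count as correctly identified, and lets a subject with no other fluorescent specimen be scored as an ICG success.

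The size cannot be derived from the documents. At assumed node-free rates of 1% to 5% of about 75 specimens, roughly 0.75 to 3.75 specimens would be miscounted. Each reclassified subject would cost 2.5 percentage points. These figures rest on the assumed rates, on independence between specimens, and on the mean of 1.87 carrying over to ICG used alone.

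Severity is minor. The study is an observational pilot with a descriptive analysis and no success threshold, so no formal decision turns on one or two subjects. The change is worth making because it is cheap and gives the word *correctly* in the primary endpoint a definite meaning.

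**What to change.** - **Sections 1.2 and 8.3:** count a fluorescent specimen as correctly identified only if the routine pathology report confirms lymph node tissue in it, recorded as yes or no. Require at least one such specimen for patient-level success.
- **Section 10.4:** allow this one field to be completed when the report is issued. Align the wording in 7.4.4.
- **Unit of counting:** keep the surgeon's count of fluorescent nodes.
- **Sensitivity analysis:** report the unconfirmed operating-room count alongside.

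The cost is one delayed field per specimen and a possibly slightly lower success rate. The documents do not describe the pathology report. That it exists is inferred from 3.1, where the biopsy is planned standard care, and from section 2.0, where node status guides treatment. The sample size and the operative procedure do not change. If the uploaded form already holds the field, only the wording of these sections needs to change.

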10.5 Individuals reviewing the data

Data will be reviewed by the PI. Adverse reactions to ICG are extremely rare, and have occurred with higher doses of ICG in subjects undergoing retinal angiography. No adverse reactions were seen in the prior study with 87 subjects, and none have been reported in the literature concerning sentinel node biopsy with ICG.

10.6 Frequency of review of cumulative data

Data will be reviewed monthly.

10.7 Statistical tests

The number of subjects planned for this study is relatively small, and given the very low complication rate seen in the prior study, statistical analysis will not be meaningful.

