1.3 Secondary Study Endpoints

Secondary endpoints include adverse events related to ICG and operative time for sentinel node biopsy.

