2.1 Previous Data

Multiple centers have published their experience with fluorescence imaging to identify sentinel nodes, in both melanoma and breast cancer.¹⁻⁴ Ballardini et al⁵ found that ICG and tech99 are equivalent in identifying sentinel nodes in patients with breast cancer, and they suggest that ICG can be used alone. In our recently completed SPY trial, 89 subjects were enrolled and received tech99, MB and ICG. The tech99 identified a mean of 1.89 sentinel nodes per patient, ICG a mean of 1.87 and MB a mean of 0.71 sentinel nodes. The ICG was well tolerated, with no adverse effects noted. A drawback to the ICG is that the fluorescent signal is visible through the skin only 47% of the time. If the nodal basin is predictable, such as for an extremity melanoma or a breast cancer, we can reasonably proceed with dissection in the predicted basin. Truncal melanomas however, do not have predictable drainage and therefore the lack of visibility is problematic for using ICG alone.

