8.0 Subject Numbers and Statistical Plan

8.1 Number of Subjects

A total of 40 subjects will be recruited into this study (we estimate we will enroll 20 subjects from Penn State Hershey Medical Center and 20 between Vasser Brother's Medical Center and Emory University School of Medicine.).

The learning curve for sentinel node biopsy is 5 cases. In order to insure that the data collected accurately represents the effectiveness of the SPY machine, each surgeon will have the goal of enrolling at least 8 subjects into the study.

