11.0 Risks

- Loss of confidentiality
- Adverse reactions to ICG are extremely rare, and none occurred in the prior trial with 87 subjects.
- Anaphylactic reactions, urticarial reactions and headache have been reported rarely in some patients.
- The risks of sentinel node biopsy are usual care as the subjects will undergo the biopsy regardless of their participation in the research. However, there is the possible risk of longer surgery, with a maximum of 30 additional minutes under anesthesia. This added time is of no consequence to the patient and carries an unmeasurable risk. Inaccurate identification of the sentinel node may occur equally in patients both on and off this study, therefore the risk in this study is no greater than usual care. The false negative rate in identifying sentinel nodes is 8%. Tech99 is used as a backup in this study in the event that the sentinel node cannot be identified with ICG.

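### The secondary safety endpoint (ICG-related adverse events) has no stated summary; a small sample and a low prior rate justify omitting a test but not an exact interval, since 0 of 40 leaves rates up to 8.8% open (two-sided 95%)

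*Combined protocol and SAP*

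**What the plan says.** Section 1.3 makes safety an endpoint: "Secondary endpoints include adverse events related to ICG and operative time for sentinel node biopsy".

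Section 8.3 makes the analysis descriptive. It then names nodes per patient found with ICG alone, patients in whom ICG alone succeeded, and each surgeon's success rate over time. It does not name adverse events.

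Section 10.7, the statistical-tests item of the data and safety monitoring plan, gives two reasons against analysis. The first is that relatively few subjects are planned. The second follows in the same sentence: "given the very low complication rate seen in the prior study, statistical analysis will not be meaningful".

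The planned size is in section 8.1: "A total of 40 subjects will be recruited into this study". Section 8.2 calls it a sample of convenience, with no precision target.

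The prior trial is described in three places:

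- Section 2.1: "89 subjects were enrolled and received tech99, MB and ICG", and later in the same paragraph "The ICG was well tolerated, with no adverse effects noted".
- Section 10.5: "No adverse reactions were seen in the prior study with 87 subjects".
- Section 11.0: "Adverse reactions to ICG are extremely rare, and none occurred in the prior trial with 87 subjects".

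Safety monitoring itself is provided for. Intraoperative adverse events are reviewed whether or not they are attributed to ICG (10.2), collected on case report forms (10.3), and reviewed monthly (10.6). A grade 4 or 5 event suspends the research (10.8).

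**The concern.** A named secondary endpoint should have a stated numerator, denominator and summary. Here the results section is silent, and the only statistical remark on safety is that analysis would not be meaningful.

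Both reasons in 10.7 argue against a test: with few subjects and rare events, a test has little power, and there is no comparator to test against. Neither argues against an estimate. When the sample is small and the count is likely to be zero, the upper confidence limit is the informative part of the result, because it shows which rates the data have not ruled out.

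Without it, the likely report is a bare statement that no ICG-related events occurred. A reader cannot tell from that how much reassurance 40 subjects provide. The denominator also needs stating. Section 7.2.2 allows fallback to the gamma probe when fluorescence finds no node. Those subjects have still been given ICG and belong in the safety count, although they are failures for the efficacy summary.

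**Working it through.** The protocol gives no confidence limit, alpha or precision target for safety, so it has no figure to reproduce. The 95% level below is an assumption.

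**Inputs.** Planned subjects: 40 (8.1), all assumed to receive ICG. Prior trial: 0 events in 89 (2.1) or 0 events in 87 (10.5, 11.0).

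**Upper limit when no events are seen.** The exact (Clopper-Pearson) two-sided 95% upper limit for 0 events in n subjects solves (1 − p)^n = 0.025, so p = 1 − 0.025^(1/n). The one-sided 95% limit is 1 − 0.05^(1/n). The rule of three, 3/n, is a rough check.

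| Result | Exact two-sided 95% | Exact one-sided 95% | 3/n |
|---|---|---|---|
| 0/40 (this trial) | 1 − 0.025^(1/40) = 8.81% | 7.22% | 7.50% |
| 0/87 (prior, 10.5 and 11.0) | 1 − 0.025^(1/87) = 4.15% | 3.38% | 3.45% |
| 0/89 (prior, 2.1) | 1 − 0.025^(1/89) = 4.06% | 3.31% | 3.37% |

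The choice of limit matters somewhat (8.8% against 7.2% for this trial), but either way a clean result in 40 subjects leaves a rate of several per cent open.

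**Chance of a clean result when the true rate is not zero.** P(no events in 40) = (1 − p)^40:

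- p = 1%: 0.99^40 = 0.669, so 67%.
- p = 2%: 0.98^40 = 0.446, so 45%.
- p = 5%: 0.95^40 = 0.129, so 13%.

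**Effect of the 89/87 discrepancy.** 4.15% − 4.06% = 0.09 percentage points. It does not change the reading of the prior result.

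**Pooling.** No pooled limit is given. It would require the prior trial's ICG dose and route to match this trial's, and the protocol does not state them.

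**The case against.** The best defence is that 10.7 sits in the monitoring plan under statistical tests, and in that place it says only that formal testing of rare events in a small study would tell us little. That is right. The protocol also gives small numbers as its first reason, so it does not rest on the prior result alone. Section 8.3 calls the analysis descriptive, and a count of events is descriptive. Collection, monthly review, the suspension trigger, causality assessment (19.3) and FDA and IRB reporting (19.4, 19.5) all remain. A reader might infer that the plan abandons safety analysis altogether; these provisions show that it does not. They do not, however, say how the endpoint will be summarised or over which subjects, and that gap stands.

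A reader might also infer from 89 against 87 that two exposed subjects were left out of the safety statement, perhaps because they had reactions. The documents do not support that. Section 2.1 describes the trial of 89 and reports no adverse effects in it, so zero events are reported under both denominators. What remains is an unexplained inconsistency in reporting.

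Nor does the protocol present ICG as free of risk: section 11.0 lists anaphylactic and urticarial reactions and headache as rare reports. Section 10.5 rests its view of rarity on wider experience as well as the prior trial. That wider experience cannot be checked from these documents.

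**Conclusion.** The point holds in a limited form. A secondary endpoint has no stated summary, and the reasons in 10.7 support omitting a test but not an estimate. If all 40 subjects receive ICG and none has a related event, rates up to 8.8% remain compatible with the data (exact two-sided, 95% level assumed); fewer exposed subjects would raise that limit. This is a worthwhile, low-cost improvement to reporting. It does not affect the design, the primary endpoint or the safety monitoring.

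The 89/87 conflict is real and should be corrected, but as a matter of consistency only.

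**What to change.** 1. Reword 10.7 to say that no hypothesis test of adverse events will be done, because the study is small and events are expected to be rare.
2. Add to 8.3 that ICG-related adverse events will be reported as the number of subjects with at least one such event over all subjects given ICG, including those in whom the gamma probe was needed, with an exact two-sided 95% confidence interval.
3. Reconcile the prior trial's denominator across 2.1, 10.5 and 11.0, with a short explanation of the difference. In 11.0, give the prior result as zero of the confirmed number with its upper limit (4.1% for 89, 4.2% for 87).
4. Report no figure pooled with the prior trial unless its dose and route are shown to match.

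The cost is a few sentences and one line of output, with no change to sample size or conduct. The downside is that the safety statement reads slightly less favourably than a bare zero.

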10.8 Suspension of research

Any grade 4 or 5 adverse event that occurs in a subject will trigger a suspension of research.

11.0 Risks

- Loss of confidentiality
- Adverse reactions to ICG are extremely rare, and none occurred in the prior trial with 87 subjects.
- Anaphylactic reactions, urticarial reactions and headache have been reported rarely in some patients.
- The risks of sentinel node biopsy are usual care as the subjects will undergo the biopsy regardless of their participation in the research. However, there is the possible risk of longer surgery, with a maximum of 30 additional minutes under anesthesia. This added time is of no consequence to the patient and carries an unmeasurable risk. Inaccurate identification of the sentinel node may occur equally in patients both on and off this study, therefore the risk in this study is no greater than usual care. The false negative rate in identifying sentinel nodes is 8%. Tech99 is used as a backup in this study in the event that the sentinel node cannot be identified with ICG.

12.0 Potential Benefits to Subjects and Others

12.1 Potential Benefits to Subjects

There are no direct benefits to the subjects.

12.2 Potential Benefits to Others

We may be able to define a group of patients who can have sentinel node localization with ICG and fluorescence imaging alone, avoiding the use of tech99. This may reduce costs, and would simplify patient care preoperatively.

13.0 Sharing Results with Subjects

Individual subjects can be told about the success of ICG during their own procedure. General study results will not be shared with subjects.

14.0 Subject Stipend (Compensation) and/or Travel Reimbursements

None

15.0 Economic Burden to Subjects

15.1 Costs

The sponsor will provide the ICG directly to HMC, Vassar Brother's Medical Center, and Emory University School of Medicine. Each institution will provide the ICG to the study patients. Subjects will be charged for Technetium 99. Subjects not enrolled in this study would be charged for blue dye, or for ICG if used in non-study patients, thus a charge for dye and injection is a usual part of the procedure.

